## 8.2.3 Time to first occurrence of treatment-emergent ADAb positivity

Study participants will be considered to have an event at the first ADAb sampling time point with ADAb positive status in the entire treatment period if the participant is Baseline ADAb negative or first ADAb sampling time point with fold difference increase from Baseline > 2.1 if participant is Baseline ADAb positive. Study participants who are never treatmentemergent ADAb positive will be censored at the date of the last evaluable (not missing, not inconclusive) ADAb sample or on date of first CZP if no evaluable post-treatment ADAb samples. In case of Baseline ADAb positivity present in more than 10% of the study participants, the table will be produced separately for ADAb participant category 2 (induced) and 5 (boosted).

- Summary tables based on Kaplan-Meier (KM) estimates will be produced.
- Kaplan-Meier plots of time to first treatment-emergent ADAb positivity will also be produced separately for the CZP doses (Original CZP dose, Reduced CZP dose). All available data timepoints will be included.

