## 8.2.1 Participant ADAb classification

Study participants from the SS will be classified based on their baseline and treatment-emergent ADAb status (Table 8–2). Classification will be done separately for two time periods of interest: (1) using the study participants' data for the entire study treatment period and (2) using the study participants' data up to and including Week 24 (to facilitate comparison with adult RA data from study RA0138 in the Updated Week 24 Interim Analysis). Baseline ADAb values are defined as the latest (not missing, not inconclusive) measurements up to and including the date of administration of first CZP treatment.

Table 8–2: ADAb status classification at participant level

	1.	Baseline ADAb negative and treatment-emergent ADAb negative	Study participants who were negative at Baseline and negative at all sampling points post treatment until the time point of interest
71	nerit c	Bulling	Note: study participants with Baseline samples missing and negative ADAb status at all sampling points post treatment are included in this category because participants who are pre ADAb positive are expected to have ADAb positive samples post-dosing.

Table 8-2: ADAb status classification at participant level

2.	Baseline ADAb negative and treatment-emergent induced ADAb positive	Study participants who were negative at Baseline and positive at any sampling point post treatment until the timepoint of interest. This group also included study participants who had a missing Baseline sample with 1 or more positive post treatment samples.
3.	Baseline ADAb positive and treatment-emergent reduced ADAb negative	Study participants who were positive at Baseline and negative at all sampling points post treatment until the timepoint of interest.
4.	Baseline ADAb positive and treatment-emergent unaffected ADAb positive	Study participants who were positive at Baseline and were positive at any sampling point post treatment until the timepoint of interest with all titer values of the same magnitude as Baseline (i.e., less than or equal to a predefined fold increase from the Baseline value of 2.10 which is defined with the validation of the assay).

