# Change #31

Section 8.2.3, Time to first occurrence of treatment-emergent ADAb positivity was added

Study participants will be considered to have an event at the first ADAb sampling time point with ADAb positive status if the participant is pre-ADAb negative or first ADAb sampling time point with fold difference increase from Baseline > 2.1 if participant is pre-ADAb positive. Study participants who are never treatment-emergent ADAb positive will be censored at the date of the last evaluable (not missing, not inconclusive and not anomalous) ADAb sample or on date of first CZP if no evaluable post-treatment ADAb samples. In case of pre-ADAb present in more than 10% of the study participants, the table will be produced separately for ADAb participant category 2 (induced) and 5 (boosted).

Summary tables based on Kaplan-Meier (KM) estimates will be produced.

Kaplan-Meier plots of time to first treatment-emergent ADAb positivity will also be produced separately for the CZP doses (Original CZP dose, Reduced CZP dose). All available data timepoints will be included.

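### Splitting the time-to-ADAb Kaplan-Meier table by categories 2 and 5 keeps only participants who had the event, so the estimate reaches 100% by construction

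*SAP*

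**What the plan says.** SAP Section 8.2.3 sets two event rules. For participants who are ADAb negative at Baseline, the event is the first positive sample over the whole treatment period; for the others it is the "first ADAb sampling time point with fold difference increase from Baseline > 2.1 if participant is Baseline ADAb positive". Censoring covers one group only: "Study participants who are never treatmentemergent ADAb positive will be censored at the date of the last evaluable" sample, or at first CZP dose if there is no such sample after treatment. The output is Kaplan-Meier: "Summary tables based on Kaplan-Meier (KM) estimates will be produced".

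A conditional split follows. When Baseline positivity exceeds 10%, the rule is that "the table will be produced separately for ADAb participant category 2 (induced) and 5 (boosted").

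The categories come from Table 8-2 in Section 8.2.1. Category 2 is "Study participants who were negative at Baseline and positive at any sampling point post treatment until the timepoint of interest", together with participants whose Baseline sample is missing and who have at least one positive sample after treatment. Category 5 is Baseline positive with any titer more than 2.10-fold above Baseline. Category 7, treatment-emergent ADAb positive, consists of those classified as 2 or 5.

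**The concern.** A Kaplan-Meier estimate of time to conversion needs a risk set formed from what is known at the start, with those who do not convert kept in it and censored. Categories 2 and 5 are assigned only after conversion has been seen. A table restricted to them selects on the outcome, and the censoring rule stated just before has nobody left to act on.

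Immunogenicity is part of the primary objective (Section 2.1.1). If the trigger is met, the table would show cumulative positivity of 100% under both dose regimens and a median time among converters. Neither figure says how likely conversion is, and the table could not separate a regimen with 20% conversion from one with 90%.

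**Working it through.** The SAP gives no ADAb rate or precision target for this analysis, so there is no planned figure to reproduce. The check compares definitions, then follows the arithmetic.

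**Step 1: event rule against category membership** (Section 8.2.3 against Table 8-2)

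| Category | Definition in brief | Event under 8.2.3? | In the split table? |
|---|---|---|---|
| 1 | Baseline negative or missing, all later samples negative | No, censored | No |
| 2 | Baseline negative or missing, any later positive | Yes | Yes |
| 3 | Baseline positive, all later samples negative | No, censored | No |
| 4 | Baseline positive, no rise above 2.10-fold | No, censored | No |
| 5 | Baseline positive, any rise above 2.10-fold | Yes | Yes |
| 6 | Baseline positive, none positive later, some or all missing or inconclusive | No, censored | No |
| 9 | Baseline negative or missing, none positive later, some missing or inconclusive | No, censored | No |

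The last two columns coincide: the split table holds those with an event and nobody else. Categories 7, 8 and 10 are unions or overlaps of the others.

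**Step 2: the estimator when nobody is censored**

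Let n be the number in the category, d_j the events at the j-th event time and n_j the number at risk. Then S(t) = ∏(1 − d_j/n_j), with n_1 = n. Without censoring, n_{j+1} = n_j − d_j, so each factor equals n_{j+1}/n_j and the product collapses to S(t) = (number still without an event)/n. After the last event that number is 0, so 1 − S = 1. The true incidence does not enter.

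For true cumulative incidences of 30%, 50% and 70% (examples), the overstatement is 100 − 30 = 70, 100 − 50 = 50 and 100 − 70 = 30 percentage points.

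**Step 3: illustration on simulated data**

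Assumptions: N = 163 + 30 = 193; events placed on sampling visits from Week 1 to Week 48; non-converters censored at visits from Week 17 to Week 96; Baseline positivity set at 11%, 15% or 30%; conversion from 20% to 95%. Results at the 15% setting, as final 1 − S with the median in weeks:

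| Assumed conversion, Baseline neg / pos | Category 2 only | All Baseline negative | Category 5 only | All Baseline positive |
|---|---|---|---|---|
| 20% / 20% | 1.000; 17 | 0.253; not reached (36 of 168) | 1.000; 17 | 0.124; not reached (3 of 25) |
| 40% / 30% | 1.000; 24 | 0.520; 48 (70 of 162) | 1.000; 24 | 0.377; not reached (9 of 31) |
| 70% / 50% | 1.000; 24 | 0.715; 40 (107 of 169) | 1.000; 24 | 0.379; not reached (8 of 24) |
| 95% / 90% | 1.000; 16 | 0.954; 24 (153 of 165) | 1.000; 24 | 1.000; 24 (25 of 28) |

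In all 12 settings both restricted estimates ended at 1.000, with medians between 12 and 24 weeks. The whole-stratum estimates moved with the assumed conversion. Some exceed the simple proportion (0.520 against 70/162 = 0.432) because only non-converters are censored in this set-up. At the 11% setting some draws fell below the 10% trigger. Neither feature affects the result in Step 2.

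**The case against.** The strongest reply is that the sentence can be read kindly. The event and censoring rules for everyone come just before it, it does not say the table is restricted to those categories, and induced and boosted could simply name the event types within the Baseline-negative and Baseline-positive strata. That is probably the intent. But the text names participant categories 2 and 5, a defined variable with its own programming aid (Table 8-3), and a programmer following it would filter on that variable. The kinder reading needs words that are not there.

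A second reply is that exactly 100% is too absolute. A category 2 or 5 member could lack a counted event in three ways: a first positive at safety follow-up, which counts for classification; conversion after a dose change, outside the data kept for that dose group; or a missing Baseline sample, which the event rule does not name. If such a person had the longest follow-up, the curve would stop short of 100%. These cases arise from mismatched windows or wording. Section 8.2 uses Final Visit data, Section 8.2.3 refers to the entire treatment period, and its censoring rule covers only the never-positive. Even where an exception occurs, the selection on outcome remains.

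A third reply stands as a limit on the consequence. Section 8.2.2 reports treatment-emergent incidence over all participants except those inconclusive or missing, and the Kaplan-Meier plots are split by dose, not by category. Time to first positivity is also not a listed primary variable; those are ADAb levels at Weeks 16 and 48 (Section 2.2.1.1). The true rate would therefore be visible elsewhere, but that does not make the table valid.

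**Conclusion.** The concern holds. As written, the conditional table conditions on the event: its cumulative estimate ends at 100% in each category and dose group, apart from the marginal window mismatches above, and its median describes converters only. That rests on the SAP's own definitions and on no assumed rate. The 30 to 70 point overstatement is an example, since the SAP states no incidence. The defect takes effect only if Baseline positivity exceeds 10%, which the SAP neither predicts nor rules out, and it is confined to this table.

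**What to change.** Replace the split in Section 8.2.3 with one by Baseline ADAb status. If the 10% trigger is met, produce the table separately for participants who are Baseline negative or missing (event: first positive sample) and for those who are Baseline positive (event: first titer rise above 2.1-fold), with all participants who have no event kept at risk and censored by the rule already given.

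Placing missing-Baseline participants with the negatives follows Table 8-2 and fills a gap in the present event rule. The cost is one SAP sentence and the matching programming change. No new data are needed.

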## 8.2.4 ECLIA vs ELISA samples

In line with \_\_\_\_\_\_ response, the proportion of study participants and the proportion of ADAb samples with sufficient volume for re-analysis with the ECLIA method out of all ADAb samples initially analyzed with the ELISA method were summarized for the Updated Week 24 Interim analysis only.

First, the number and percentage of study participants with at least one ADAb sample reanalyzed using the ECLIA method (after previous analysis using the ELISA method) were presented. For this percentage, the denominator is the number of study participants with at least one non-missing ADAb result from the ELISA method and the numerator is the number of study participants with at least one non-missing ADAb result from the ECLIA method that had also been analyzed with the ELISA method previously. (BLQ is considered a non-missing result.)

Second, the number and percentage of baseline and post-baseline ADAb samples that were re-analyzed using the ECLIA method (after previous analysis using the ELISA method) were presented separately. For the percentage of baseline and post-baseline re-analyzed ADAb samples, the denominator is the number of baseline or post-baseline ADAb samples with non-missing ELISA results, respectively. The numerator is the number of baseline or post-baseline ADAb samples, respectively, with non-missing ECLIA results previously where the same ADAb sample had previously been analyzed with the ELISA method. (Below LLOQ is considered a non-missing result.)

Additionally, the proportion of study participants and the proportion of ADAb samples with sufficient volume for re-analysis with the ECLIA method out of all ADAb samples analyzed with the ECLIA method (either originally or via re-analysis) were summarized.

First, the number and percentage of study participants with at least one ADAb sample reanalyzed using the ECLIA method (after previous analysis using the ELISA method) were presented. For this percentage, the denominator is the number of study participants with at least one non-missing ADAb sample that was analyzed using the ECLIA method (either originally or via re-analyses). The numerator is the number of study participants with at least one non-missing ADAb result from the ECLIA method for a sample that had also been analyzed with the ELISA method previously. Also, the number and percentage of study participants that did not have any ADAb sample re-analyzed with the ECLIA method were presented. The denominator is the same, but the numerator is the number of study participants for whom all non-missing ADAb results obtained using the ECLIA method were on samples that had never been analyzed using the ELISA method. (Below LLOQ is considered a non-missing result.)

Second, the number and percentage of baseline and post-baseline ADAb samples that were analyzed using the ECLIA method (after previous analysis using the ELISA method) were presented. For this percentage, the denominator is the number of non-missing baseline or post-baseline ADAb results, respectively, that were obtained using the ECLIA method (either originally or via re-analysis). The numerator is the number of those non-missing baseline or post-baseline ADAb results, respectively, that were obtained by re-analysis with the ECLIA method, after having been analyzed by the ELISA method previously. Also, the number and

Confidential

percentage of those baseline or post-baseline samples, respectively, that were not re-analyzed with the ECLIA method (out of those analyzed with the ECLIA method) were presented. The denominator is the same for each, respectively, but the numerator is the number of those nonmissing baseline or post-baseline ADAb results, respectively, for samples that were only ever analyzed using the ECLIA method. (Below LLOQ is considered a non-missing result.)

All summaries were provided for the Safety Set and presented for Original CZP Dose, Reduced CZP Dose, Complete Original CZP Dose and Complete Reduced CZP Dose by baseline weight.

# 8.3

CZP plasma concentrations, anti-CZP antibody titers, and PedACR response

ibed in this section that include an efficacy endpoint will and the PK-PPS. Individual participants place ADAb titers, and maximum and will be produced. The plots described in this section that include an efficacy endpoint will be generated on the FAS, otherwise on the PK-PPS. Individual participants plots displaying CZP plasma concentrations, ADAb titers, and maximum PedACR response (the highest PedACR response at a given visit) will be produced by visit on the same plot. At each time point, the maximum PedACR response at that visit will be plotted on a linear scale. CZP plasma concentration will be plotted on a (natural) log scale and ADAb titer will be plotted on a log 2 scale. CZP dosing and ADAb inconclusive values will be flagged in this plot. A vertical line will be plotted when dose was changed for the study participant. For each study participant, the category of ADAb participant status and demographic information at baseline (body weight and age) will be displayed.

Multi-panel spaghetti plots of individual participant (natural) log CZP plasma concentration by visit will be produced separately for each CZP dose (Original CZP dose, Reduced CZP dose) and ADAb titer classification and ADAb participant classification for the PK-PPS. Concomitant MTX use will be shown in different line colors and CZP concentrations for which ADAb positive samples were positive will be plotted with a red dot. These individual plots will be repeated replacing CZP plasma concentration with maximum PedACR response (linear scale) on the FAS.

Scatter plots of the plasma CZP concentration at each visit with different colors/symbols depending on ADAb participant classification and ADAb titer classification will be produced separately for the doses (Original CZP Dose, Reduced CZP Dose) for the PK-PPS.

## PopPK analyses 8.4

Plasma concentrations will be used to build a PopPK model with the nonlinear mixed-effect modeling (NONMEM) software. Details of the PopPK modeling procedures will be described in a separate data analysis plan. This analysis was generated for the Updated Week 24 Interim analysis only.

All study participants in the SS will be included in the safety analyses. In addition to the safety summaries described below, all safety results will be listed by study participants.

Confidential Page 53 of 252

## 9.1 Extent of exposure

Over the course of the RA0043 study, study participants follow one of 5 dosing scenarios for CZP exposure:

Table 9–1: Dosing periods

Starting the study taking:	1st dosing period (of variable length)	2 nd dosing period (of variable length)	3 rd dosing period (of variable length)
Reduced CZP dose	Reduced CZP (A)		2
	Reduced CZP (B) ->	Original CZP (E)	S)O:
Original CZP dose	Original CZP (F)		ensie
	Original CZP (G) ->	Reduced CZP (C)	et
	Original CZP (H) ->	Reduced CZP (D) ->	Original CZP (J)

The extent of exposure to study drug will be evaluated by summarizing the total amount of CZP received in mg and the total duration of exposure in days. Total duration of exposure will be calculated using this general formula as: the Date of Last Dose of study medication – Date of First Dose of study medication + 14 days if administration of CZP is Q2W, +28 days if administration of CZP is Q4W. Dosing gaps (which occur between 2 CZP doses) are not considered in (does not reduce) the duration of exposure calculation.

Duration of exposure will be calculated as appropriate for each of the following dosing periods:

A: use the general formula;

B: Date of Escalation – Date of First Dose;

C: Date of Last Dose – Date of Dose Reduction +14 or 28 days depending on administration of CZP;

D: Date of Escalation – Date of Reduction;

E: Date of Last Dose Date of Dose Escalation + 14 or 28 days depending on administration of CZP;

F: use the general formula: see A above

G: Date of Dose Reduction – Date of First Dose;

H: Date of Dose Reduction – Date of First Dose;

J. Date of Last Dose – Date of Dose Escalation + 14 or 28 days depending on administration of CZP

Duration of exposure was calculated as are:

Duration of exposure was calculated as appropriate for each of the following CZP Dose groups for the Updated Week 24 Interim Analysis but will only be calculated for Any CZP Dose, Reduced CZP Dose and Original CZP Doze for the final analysis:

- Any CZP Dose: includes the exposure to all CZP doses for all treated study participants; the exposure period is calculated using the general formula.
- Dose for all study participants without dose escalation; and Original CZP Dose: includes period of exposure to the Original CZP Dose for all study participants enrolled on the Original CZP Dose; use the following formulas:

  Period F for study participants without dose reduction;

  Period G for study participants with '

  Period H Perio
- - Period H for study participants with dose reduction and dose escalation.
- Complete Reduced CZP Dose: includes all periods of exposure to Reduced CZP Dose for all study participants (periods A, B, C and D); use the following formulas:
  - Period A for study participants enrolled on Reduced CZP Dose without dose escalation;
  - Period B for study participants enrolled on Reduced CZP Dose with dose escalation;
  - Period C for study participants enrolled on Original CZP Dose with dose reduction and without dose escalation; and
  - Period D for study participants enrolled on Original CZP Dose with dose reduction and dose escalation.
- Complete Original CZP Dose: includes all periods of exposure to Original CZP dose for all study participants (periods E, F, G H and J); use the following formulas:
  - Period E for study participants enrolled on Reduced CZP Dose with dose escalation;
  - Period F for study participants enrolled on Original CZP Dose without dose reduction;
  - Period G for study participants enrolled on Original CZP Dose with dose reduction and without dose escalation; and
  - Period H+J for study participants enrolled on Original CZP Dose with dose reduction and dose escalation.

  - Period G for study participants with dose reduction and without dose escalation; and
  - Period H for study participants with dose reduction and dose escalation.

- Complete Reduced CZP Dose: includes time at risk during all periods of exposure to Reduced CZP Dose for all study participants (periods A, B, C and D); use the following formulas:
  - Period A for study participants enrolled on Reduced CZP Dose without dose escalation;
  - Period B for study participants enrolled on Reduced CZP Dose with dose escalation;
  - Period C for study participants enrolled on Original CZP Dose with dose reduction and without dose escalation; and
  - Period D for study participants enrolled on Original CZP Dose with dose reduction and dose escalation.
- Complete Original CZP Dose: includes all time at risk during all periods of exposure to Original CZP dose for all study participants (periods E, F, G H and J); use the following formulas:
  - Period E for study participants enrolled on Reduced CZP Dose with dose escalation;
  - Period F for study participants enrolled on Original CZP Dose without dose reduction;
  - Period G for study participants enrolled on Original CZP Dose with dose reduction and without dose escalation; and
  - Period H+J for study participants enrolled on Original CZP Dose with dose reduction and dose escalation.

The extent of study drug exposure will be summarized for the Reduced CZP Dose, Original CZP Dose, and Any CZP Dose groups. Exposure over time will be presented as follows: >0 months,  $\geq 6$  months,  $\geq 12$  months,  $\geq 24$  months,  $\geq 36$  months,  $\geq 48$  months, and  $\geq 96$  months. In line with

response, the extent of study drug exposure as well as exposure over time were presented by Complete Original CZP Dose and Complete Reduced CZP Dose.

Study medication administration will be listed.

